# 9.5. Other Reportable Events

Certain events should be reported to the Sponsor as Other Reportable Events. These include the following:

- Pregnancy exposure (a patient becomes pregnant while taking study drug)
  - Patients who are pregnant at Screening and/or Day -1 are not permitted to participate in this study. Nabriva Therapeutics DAC or their representative must be notified of any female patient (or the partner of a male patient) who becomes pregnant during the study. Although pregnancy is not technically an AE, all pregnancies must be followed to conclusion to determine their outcome. This information is important for both drug safety and public health concerns. It is the responsibility of the Investigator or designee to report any pregnancy that occurs during this study to Nabriva Therapeutics DAC or their representative.
- Lactation exposure (ie, the patient was taking study drug while nursing an infant)
- Accidental exposure (someone other than the study patient was exposed to study drug)
- Overdose (the patient received more than the prescribed dose of study drug within a given timeframe)
- Other medication errors that potentially place patients at a greater risk of harm than was previously known or recognized (eg, study drug was administered by an incorrect route)

#### 10. DRUG SUPPLIES

## **10.1.** Description of Drug Products

The active substance being investigated in this study is lefamulin (BC-3781), present in the drug product as the acetate salt (BC-3781.Ac). Physicochemical properties can be found in the Lefamulin Investigator's Brochure.

The IV drug product is supplied by the Sponsor in clear glass vials containing a sterile concentrate of the acetate salt of lefamulin (BC 3781.Ac) in normal saline. The content of one vial equals to 150 mg lefamulin free base. Lefamulin for IV use is constituted from one lefamulin 15 mL sterile concentrate vial into a sterile custom-manufactured 250 mL citrate buffered normal saline bag pH 5 for IV administration.

Oral lefamulin is supplied by the Sponsor as 600 mg blue, oval, film-coated, immediate-release tablets printed with "LEF 600" on one side.

Details of the qualitative and quantitative composition of lefamulin IV drug product and lefamulin 600-mg IR tablets are provided in the Lefamulin Investigator's Brochure.

# 10.2. Packaging and Labeling

Lefamulin will be packaged and labeled in accordance with the applicable regulatory authority requirements.

# 10.3. Storage of Study Drugs

Access to all study drugs must be restricted to designated study personnel throughout the study.

02 November 2021 37 Confidential

The lefamulin IV drug product is supplied in clear glass vials. The shelf life of the lefamulin concentrate vials is 48 months at 2 to 8°C. Commercial supplies of citrate buffered normal saline will be used.

The lefamulin 600-mg IR tablets will be supplied in a high-density polyethylene bottle with 30 tablets per bottle. The shelf life of the IR tablets is at least 48 months at controlled room temperature (15°C to 25°C).

Temperature excursions must be reported to the Sponsor.

## 10.4. Product Accountability

The Investigator is responsible for study drug accountability, reconciliation, and record maintenance. In accordance with all applicable regulatory requirements, the Investigator or designated study site personnel must maintain study drug accountability records throughout the course of the study. This person(s) will document the amount of study drug received from the supplier, the amounts dispensed to patients as well as lot numbers and expiration / retest date of study medications. At conclusion of the study, any unused study drug will be destroyed at the site after approval from the Sponsor. If no supplies remain, this will be recorded in the drug accountability section of the final monitoring report.

## 10.5. Compliance

Study personnel will supervise, observe, and record all study drug dosing of each patient while he/she is an inpatient at the CRU.

### **10.6.** Treatment of Overdose

As study personnel are administering and documenting all doses in the study, the risk of overdose is considered to be low.

No specific antidote to lefamulin is known. Any signs or symptoms of a possible overdose will be treated supportively. In the case of an emergency, standard emergency procedures will be employed.

# 10.7. Occupational Safety

Lefamulin is not expected to pose a significant occupational safety risk to site staff under normal conditions of use and administration. Material Safety Data Sheets describing occupational hazards and recommended handling precautions will be either provided to the Investigator, where this is required by local laws, or are available upon request from Nabriva Therapeutics.

In line with good handling of chemical products, precautions are to be taken to avoid eye contact, and generating aerosols or mists. In the case of unintentional occupational exposure, any signs or symptoms should be treated appropriately, and the Sponsor notified.

#### 11. STATISTICAL ANALYSIS

### 11.1. Sample Size Determination

Target enrollment for this study will be 12 patients.

### 11.2. Analysis Sets

- Safety analysis set: All patients who received any dose of lefamulin.
- Pharmacokinetic analysis set: All patients who receive any dose of lefamulin and have an evaluable PK profile.

### 11.3. Variables for Analysis

#### 11.3.1. Pharmacokinetic Analysis Variables

Appropriate non-compartmental techniques will be used to obtain estimates, including but not limited to, the following PK parameters in plasma for lefamulin and its metabolite BC-8041 when possible and appropriate:  $T_{lag}$  (oral dose only),  $T_{max}$ ,  $C_{max}$ ,  $AUC_{(0-last)}$ ,  $AUC_{(0-24h)}$ ,  $AUC_{(0-inf)}$ ,  $AUC_{(0-in$ 

A complete description of the PK analysis variables will be presented in the Statistical Analysis Plan (SAP).

#### 11.3.2. Safety Analysis Variables

Safety and tolerability will be assessed by monitoring AEs and concomitant medications, clinical chemistry and hematology laboratory assessments, vital signs, ECG results, and physical examination findings. A complete description of the safety analysis variables will be presented in the SAP.

# 11.4. Pharmacokinetic Analysis

Presentation of PK data will be descriptive in nature and will be presented by treatment.

# 11.5. Statistical Analysis

A separate SAP will be developed and approved before the final analyses. A complete description of the analyses will be provided in the SAP.

Categorical data will be summarized with counts and percentages and continuous variables with N, mean, coefficient of variation (CV), median, standard deviation, and range. In addition, PK parameters will be summarized with the geometric mean and geometric CV.

Further details of the statistical analysis will be provided in a study-specific SAP, which will include, but are not limited to:

- Definition of analysis populations
- Details of planned analysis of primary and secondary variables as well as safety

02 November 2021 39 Confidential

• Data handling conventions

## 11.6. Safety Analysis

Descriptive summaries and listings of individual patient safety data will be presented by treatment.

Safety will be evaluated in the Safety Analysis Set by presenting summaries of AEs, routine clinical laboratory parameters, ECG results, and vital sign parameters by treatment.

Adverse events will be coded using the Medical Dictionary for Regulatory Activities (MedDRA). Summary tables will be provided for all TEAEs. A TEAE is defined as an AE with a start date and time on or after study drug administration. The number and percentage of patients with TEAEs will be tabulated by system organ class and MedDRA preferred term for each treatment and dose, and by severity and relationship to treatment.

Treatment-emergent AEs leading to premature discontinuation from study and serious TEAEs will be presented in a table and/or a listing.

Safety data including clinical laboratory parameters, ECG results and vital signs will be summarized by treatment and scheduled assessment. These summaries will also include change from baseline for each scheduled assessment by treatment.

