#### 7. STUDY DRUG ADMINISTRATION

#### 7.1. **Duration of Treatment**

Each patient will receive a single dose of lefamulin at 2 study periods 4 to 7 days apart.

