#### 9. ADVERSE EVENTS

#### 9.1. Definition of Adverse Events

An AE is any untoward medical occurrence in a patient or clinical investigation patient administered a pharmaceutical product and which does not necessarily have a causal relationship with this treatment. An AE can therefore be any unfavorable and unintended sign (including an abnormal laboratory finding), symptom, or disease temporally associated with the use of a medicinal (investigational) product, whether or not related to the investigational medicinal product.

Any pre-existing conditions or signs and/or symptoms present in a patient before the start of the study (ie, before informed consent) should be recorded as medical/surgical history. Any medical occurrences that are new or worsened from the time of informed consent and up to and including the final visit must be reported as AEs. All AEs must be recorded regardless of causality.

Patients will be monitored throughout the study for adverse reactions to the study medications and/or procedures at each study visit. Questions will be posed in a non-leading manner so as not to bias the response. In addition to questioning at specific time points, patients will be encouraged to spontaneously report any AEs. Any patient with an AE or clinically significant abnormal laboratory test result will be evaluated by the Investigator, or a monitoring physician, and will be treated and/or followed until the symptoms or values have resolved or are assessed as stable by the Investigator. A physician, either at the investigative site or at a nearby hospital emergency room, will administer treatment for any serious adverse events (SAEs). When appropriate, medical tests and examinations may be performed to ensure an AE has fully resolved.

Adverse events will be collected throughout the study from the time a patient signs the informed consent through the Follow-up assessment after the second dosing period. Whenever possible, a specific disease or syndrome rather than individual associated signs and symptoms should be identified by the Investigator and recorded on the eCRF. However, if an observed or reported sign or symptom is not considered a component of a specific disease or syndrome by the Investigator, it should be recorded as a separate AE on the eCRF.

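### The TEAE definition in Section 11.6 uses onset alone and does not say which dose it refers to, so worsening after a dose can go uncounted or unlinked to that dose in this two-dose crossover

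*Protocol*

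**What the plan says.** - **Definition (Section 11.6).** "A TEAE is defined as an AE with a start date and time on or after study drug administration". The sentence refers to administration in the singular, sets no end to the window and does not mention worsening.
- **Tabulation (Section 11.6).** "The number and percentage of patients with TEAEs will be tabulated by system organ class and MedDRA preferred term for each treatment and dose". The same section also calls for tables by severity and by relationship.
- **Design (Section 7.1).** "Each patient will receive a single dose of lefamulin at 2 study periods 4 to 7 days apart". One dose is IV and the other oral.
- **Collection (Section 9.1).** AEs are collected "from the time a patient signs the informed consent through the Follow-up assessment after the second dosing period", without a break between periods.
- **Reporting of worsening (Section 9.1).** The rule for what counts as an AE covers worsening: "Any medical occurrences that are new or worsened from the time of informed consent and up to and including the final visit must be reported". Signs and symptoms present "before informed consent) should be recorded as medical/surgical history".
- **What is recorded (Section 9.1).** Each AE has an onset, an end and a severity. No rule says whether a change in severity opens a new record or receives its own date.
- **Deferral (Sections 11.3.2 and 11.5).** The full description of the safety variables and the data handling conventions are left to the SAP, which is not shown.

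**The concern.** A rule based on onset alone works for a single dose given to patients with no ongoing AEs at the time. Here there are two doses, continuous AE collection, and a screening interval of up to 30 days before the first dose in which AEs are already being recorded. An event can therefore be open when a dose is given and get worse afterwards. That deterioration is what a tolerability table should show, but the definition does not pick it up.

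Safety and tolerability of the oral and IV doses is the only secondary objective (Section 4.1.2), and TEAEs are one of four descriptive summaries that serve it (Section 4.2.2). Section 3.4 expects different profiles by route, mainly gastrointestinal events after oral dosing and administration site reactions after IV dosing. A table by treatment is informative only if an event, or its worsening, can be tied to the dose that preceded it.

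**Working it through.** The plan gives no figure that bears on this point, so there is none to reproduce. The target of 12 in Section 11.1 is stated without a derivation. The check is to apply the Section 11.6 sentence to each possible timing, alongside the reporting rule in Section 9.1.

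1. **Condition present before consent, worsens after a dose.** It is medical history until it worsens, then becomes reportable under Section 9.1. It first enters as an AE at worsening, so it can carry a post-dose start and count. No gap.
2. **AE starts between consent and dose 1, worsens after dose 1.** It is already an AE with a pre-dose start. If it keeps that start, it fails the definition. If the worsening is entered as a new AE, it meets it. The protocol does not say which to do. Gap.
3. **AE starts after dose 1 and before dose 2, no later worsening.** It is a TEAE, and only one treatment has been given. No gap.
4. **AE starts after dose 1, worsens after dose 2.** It is a TEAE by its onset, but nothing ties the worsening to the second treatment unless it is re-recorded. Gap.
5. **AE starts after dose 2.** It is a TEAE. Its onset follows both administrations, and the sentence does not say which one it refers to. Ambiguity.

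Timings 1 and 2 describe the same post-dose deterioration. They are classified differently only because onset fell before or after the consent signature, which has no bearing on tolerability.

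**Size.** Input: 12 patients (Section 11.1), all assumed to receive both treatments. One patient missed or placed under the wrong treatment changes that treatment's incidence by 1/12 = 0.083, or 8.3 percentage points. The documents give no rate for events of timing 2 or 4, so the expected number of such patients cannot be derived.

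**The case against.** **Much of this can be left to the SAP.** Assigning AEs to periods in a crossover is commonly an SAP convention, and Sections 11.3.2 and 11.5 defer such detail. For attribution (timing 5) this stands: a convention there would settle the matter, and its absence from the protocol is not an error. It does not dispose of worsening. Section 11.6 states the definition outright, so an SAP that added worsening would depart from the protocol. Nor could an SAP recover the date of a severity change that was never recorded.

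**A reader might infer double counting.** Because a Period 2 onset follows both doses, one could read the rule as placing that event under both treatments. Assume equal and independent TEAE probability p in each period and 6 patients per sequence. A patient would then be counted under the Period 1 treatment with probability 1 − (1 − p)², which is 36% at p = 20% and 64% at p = 40%. Those are rates by sequence position. By treatment, the rate is [p + 1 − (1 − p)²]/2, which is (20 + 36)/2 = 28% and (40 + 64)/2 = 52%. Under these assumptions both routes rise equally, so the comparison between them is not shifted in expectation. In any case the documents do not support the reading: the sentence defines treatment-emergent status, not attribution, and nothing tells the analyst to count a Period 2 event under the Period 1 treatment.

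**A reader might also infer that worsening never counts.** Timing 1 shows otherwise. Chronic CF symptoms that predate consent can become AEs with a post-dose start. Inclusion criterion 6 requires clinical stability over the 28 days up to and including Day 1, which should make timing 2 less common. Events of that kind are still collected and would appear in the individual listings; they would be missing from the TEAE tables, not from the data.

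**Conclusion.** The point holds in a limited form. The stated definition can give a wrong count for an AE that starts between consent and the first dose and worsens after dosing. It also fails to link to the second treatment an AE that starts after dose 1 and worsens after dose 2. Both results depend on the AE keeping its original start, which the protocol neither requires nor rules out. The unspecified administration is an ambiguity that needs a clarifying phrase, no more.

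The consequence is limited to descriptive safety tables, at 8.3 points per misclassified patient if all 12 contribute to both treatments. TEAEs stand alongside laboratory, vital sign and ECG summaries without a stated ranking. The primary PK endpoint is unaffected. The correction is worth making because it is cheap and part of it concerns data capture, which cannot be mended at analysis.

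**What to change.** In Section 11.6, define a TEAE as an AE that starts, or worsens in severity, on or after the first dose. Assign it to the treatment most recently given before the onset or worsening. Let the Period 1 window, including washout, end at the Period 2 dose, and let the Period 2 window run to the final Follow-up.

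In Section 9.1, state that an AE which worsens after a dose is recorded with its own start date and time, so that the definition can be applied to the data.

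The cost is about two sentences of protocol text, a matching eCRF instruction, and an extra AE record whenever severity worsens. No visit, procedure or sample is added.

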#### 12. STUDY MONITORING

All aspects of the study will be carefully monitored by the Sponsor's authorized individuals, acting as agents of the Sponsor with respect to current Good Clinical Practice (GCP) and Standard Operating Procedures for compliance with applicable government regulations. These individuals will have access to all records necessary to ensure integrity of the data and will periodically review the progress of the study with the Principal Investigator.

Frequent communication between the study site and the Sponsor is essential to ensure that the patient safety is monitored adequately. The Investigator will make safety assessments on an ongoing basis. The Sponsor's medical monitor will review safety information from all study sites as it becomes available throughout the study.

#### 13. INSTITUTIONAL REVIEW BOARD APPROVAL

The Principal Investigator agrees to provide the Institutional Review Board (IRB) with all appropriate material, including a copy of the informed consent. The study will not be initiated until the Investigator obtains written approval of the research plan (protocol) and the informed consent document from the appropriate IRB and copies of these documents are received by Nabriva Therapeutics.

It is the Investigator's responsibility to obtain IRB approval for all subsequent major changes to the protocol, in compliance with local law. Appropriate reports on the progress of this study will be made by the Investigator to the IRB and Sponsor in accordance with applicable government regulations and in agreement with policy established by the Sponsor.

#### 14. ETHICAL CONDUCT OF THE STUDY

This clinical study will be conducted in compliance with this protocol, the guidelines of the World Medical Association Declaration of Helsinki in its revised edition (Fortaleza, Brazil, October 2013), the guidelines of International Council on Harmonisation (ICH) GCP (CPMP/ICH/135/95), European Union (EU) Clinical Trials Directive 2001/20/EC, EU Commission Directive 2005/28/EC, and Code of Federal Regulation (CFR) Title 21, CFR Part 50, 56 and 312, designated Standard Operating Procedures, and with local laws and regulations relevant to the use of new therapeutic agents in the country of conduct.

#### 15. INFORMED CONSENT

The ICH has issued guidelines to provide protection for human patients in clinical investigations. The ICH Tripartite Guideline for Good Clinical Practice establishes the general requirements for informed consent.

A properly executed, written informed consent in compliance with the terms of these guidelines shall be obtained from each patient before entering the study, or before performing any unusual or non-routine procedure in relation to the study. The purpose of the study, procedures to be carried out, and potential hazards will be described to each potential patient in non-technical terms. Patients will be required to read, voluntarily sign, and date an informed consent form summarizing the discussion at Screening, and will be assured that they may withdraw from the study at any time without jeopardizing their medical care.

Patients will sign and date one copy of the informed consent form which will be photocopied. The copy will be retained by the patient and the original will be retained on file by the Investigator. The consent form must be approved by the appropriate IRB and Sponsor before study initiation at a study site. Any subsequent changes to the approved informed consent form must be reviewed and approved by the appropriate IRB and Sponsor before implementation.

## 16. QUALITY ASSURANCE/QUALITY CONTROL

Standard Operating Procedures belonging to Nabriva Therapeutic or designee(s) will be adhered to for all activities relevant to the quality of the study and are routinely monitored by the Quality Assurance (QA) Division.

Data will undergo quality control checks before clinical database lock. Sponsor-designated, independent monitors will be responsible for the monitoring of the study and its data within the eCRFs.

A QA audit of this study may be conducted by the Sponsor or Sponsor's designee. The QA auditor will have access to all medical records, the Investigator's study-related files and correspondence, and information in the informed consent documentation of this study.

An inspection of this study may be conducted by a regulatory agency. The Investigator agrees to contact the Sponsor as soon as possible, but not later than within 1 week, upon notification of an inspection by a regulatory agency. The Investigator agrees to allow the Inspector direct access to all relevant documents and to allocate his/her time and that of study site personnel to the

02 November 2021 41 Confidential

Clinical Study Protocol NAB-BC-3781-1014

Nabriva Therapeutics Lefamulin

Inspector to discuss findings in any relevant issues. The Investigator will allow Sponsor personnel to be present as an observer during a regulatory inspection, if requested.

### 17. DATA HANDLING AND RECORD KEEPING

## 17.1. Data Handling

Electronic case report forms are produced, stored electronically, and are available to the designated study team members. Each eCRF is reviewed and signed by the Investigator. The final signed case report forms (CRFs) are provided to the Sponsor in the format as decided upon by the Sponsor, as documented in the data management plan (if applicable).

